4.2.8 Best objective response and objective response rate

For each treatment group, BoR as defined in Section 3.2.7 will be summarised by n (%) for each category (CR, PR, SD, NED, PD, NE) based on the BICR data. This will also be summarised based on the investigator-assessed data. No formal statistical analyses are planned.

ORR as defined in Section 3.2.8 will be summarised descriptively, ie, number of patients (%) by treatment group, and using logistic regression, based on the BICR data, in patients in the FAS (ITT population) with measurable disease at baseline defined according to BICR. The results of the analysis will be presented in terms of an odds ratio together with its associated profile likelihood 95% CI and p-value (based on twice the change in log-likelihood resulting from the addition of a treatment factor to the model). If there are not enough responses for a meaningful analysis using logistic regression, then a Fisher's exact test will be presented.

ORR will also be summarised based on the investigator-assessed data in the FAS (ITT population) with measurable disease at baseline defined according to investigator assessment using the same methods as for the BICR data. Any patients who experienced CR or PR which was first observed whilst receiving subsequent therapy after discontinuation of olaparib will be identified and not treated as responders per definition of BoR in Section 3.2.7.

In addition, the duration and time to onset of objective response in patients with objective response (by BICR and by investigator assessment) will be summarised by treatment group.

95% confidence intervals for median duration and median time to onset of objective response in patients with objective response (by BICR and by investigator assessment) calculated using the Kaplan Meier method will be presented by treatment group.

BoR will be presented in a by-patient listing. In addition, a listing will be prepared including objective responders (confirmed CR or PR) only.

4.2.9 Disease control rate

The DCR as defined in Section 3.2.9 will be summarised (ie, n, %) by treatment group. The DCR will be presented based on the BICR data and also the investigator recorded data.

4.2.10 Target lesion summary and other efficacy

Target lesion size, and percentage change from baseline will be summarised by treatment group and time point using descriptive statistics. Lesion data according to BICR and also by investigator assessment will be listed in by-patient listings.

Subsequent cancer therapy relative to progression will be summarised using frequency counts and percentages. The tabulation will detail any patients receiving any further therapy for cancer by time of therapy ('After progression', 'Before progression', 'No progression'). Tabulation will include the number of patients where no subsequent cancer therapy was recorded as well. Data will be presented by treatment group.

4.2.11 Patient reported outcomes

The analysis population for PRO data will be the PRO analysis set as defined in Section 2.1. Derivations and rules for transformation of PRO data are defined in Section 3.3.

Impact of olaparib on HRQoL

The impact of olaparib on HRQoL will be assessed through an analysis of the global health status / QoL gathered from items 29 and 30 of EORTC QLQ-C30.

Descriptive statistics including change from baseline score will be produced by time point for the EORTC QLQ-C30 global health status / QoL score. Results will be presented by treatment group. Arithmetic mean (\pm standard deviation) plots of scores versus time point will be produced in linear scale.

Adjusted mean change from baseline in global QoL score will be analysed using a mixed model for repeated measures (MMRM) analysis of all of the post-baseline scores for each visit and will be presented by treatment group. Only visits with at least 25% of non-missing values in both treatment arms (calculated separately by treatment arm) are included in the model. The study treatment discontinuation visit and the safety follow-up visit will be excluded from this analysis. Restricted maximum likelihood (REML) estimation will be used. The model will include randomised treatment group, visit and treatment by visit interaction as explanatory variables and the baseline QoL score as a covariate along with a baseline QoL score by visit

variable in the MODEL-Statement together with the option CLPARM=PL to compute profile likelihood CIs and p-values. Explanatory variables will be introduced using a reference cell coding (option PARAM=REFERENCE) while the option REF= will be used to identify the reference. The following provides sample SAS code for implementing the analysis:

```
CCI  
[Redacted SAS code]
```

If the overall improvement rate is < 5%, no analysis will be performed (note that if the response rate in only one of the treatment groups is < 5% but \geq 5% in the other treatment group then the analysis will still be performed). If the overall response rate is low (< 20%) a Fisher's exact test (for an example SAS code see below) will be considered and mid p-values used. The results of the analysis will be presented in terms of an odds ratio together with its associated profile likelihood CIs and p-values (based on twice the change in log-likelihood resulting from the addition of a treatment factor to the model).

```
CCI  
[Redacted SAS code]
```

In addition, a summary table of EORTC QLQ-C30 global QoL score best overall QoL response will be provided (improvement, deterioration, no change).

Compliance

The EORTC QLQ-C30 and CCI compliance (overall compliance and by visit compliance, separately for each form) will be summarised and presented by treatment group.

4.2.12 Exploratory analyses

```
CCI  
[Redacted SAS code]
```

- CCI [REDACTED]

[REDACTED]

| [REDACTED]

| [REDACTED]

| [REDACTED]

| [REDACTED]

| [REDACTED]

[REDACTED]

[REDACTED]

[REDACTED]

[REDACTED]

| [REDACTED]

| [REDACTED]

| [REDACTED]

| [REDACTED]

| [REDACTED]

| [REDACTED]

CCI
[Redacted]

[Redacted]

[Redacted]

[Redacted]

[Redacted]

[Redacted]

[Redacted]

[Redacted]

[Redacted]

[Redacted]

CCI [Redacted]

[Redacted]

[Redacted]

CCI [Redacted]

CCI

[figure not shown]
CCI

CCI

CCI

CCI

4.2.13 Safety

Safety data will be summarised and listed only. No formal statistical analyses will be performed on the safety data. All safety data will be summarised by actual treatment group (olaparib or placebo). However, some listings such as AEs listings will display the actual dose the patient received at onset of an AE.

Adverse events

All AEs, both in terms of Medical Dictionary for Regulatory Activities (MedDRA) preferred term (PT) and Common Toxicity Criteria for Adverse Events (CTCAE) grade, will be listed and summarised descriptively by count (n) and percentage (%) for each treatment group. MedDRA dictionary will be used for coding. Any AE occurring before olaparib/placebo treatment (ie, before Study Day 1) will be included in the AE listings, but will not be included in the summary tables (unless otherwise stated). These will be referred to as 'pre-treatment'.

The summary tables will include all AEs that occurred after the start of treatment up until the end of the 30 day follow-up period. The 30 day follow-up period will be defined as 30 days following discontinuation of olaparib/placebo treatment. Any untoward event occurring subsequent to the 30-day follow-up AE reporting period that the investigator assesses as possibly related to the study treatment will also be included in the AE listings, but not in the summary tables.

All reported AEs will be listed along with the date of onset, date of resolution (if AE is resolved), investigator's assessment of severity and relationship to study drug. Frequencies

and percentages of patients reporting each PT will be presented (ie, multiple events per patient will not be accounted for apart from on the episode level summaries).

Summary information (the number and percent of patients by actual treatment) will be tabulated for:

- All AEs
- All AEs causally related to study medication
- AEs with CTCAE grade 3 or higher
- AEs with CTCAE grade 3 or higher, causally related to study medication
- AEs leading to dose modification of olaparib/placebo
- AEs leading to dose interruption of olaparib/placebo
- AEs leading to dose reduction of olaparib/placebo
- AEs with outcome of death
- AEs with outcome of death causally related to study medication
- All SAEs
- All SAEs causally related to study medication
- DAEs
- AEs leading to discontinuation of olaparib/placebo, causally related to study medication

An overall summary of the number and percentage of patients in each category will be presented.

In addition, a truncated AE table of most common AEs, showing all events that occur in at least 5% of patients overall will be summarised by PT, by decreasing frequency. This cut-off may be modified after review of the data. Also, a truncated AE table of most common non-serious AEs, showing events that occur in at least 5% of patients on the PT level in at least one treatment group will be summarised by SOC and PT, by decreasing frequency.

Each AE event rate (per 1000 patient years) will be summarised by system organ class (SOC) and also by PT within each SOC. The event rate will be calculated as the number of patients with an AE in that SOC or with that PT divided by the sum of the duration of therapy (for

patients without such an event) and the time to the AE (for patients with such an event) in each group multiplied by 1000. The denominator defines the time at risk for an event with:

- Duration of therapy (days) calculated as:
MINIMUM([date of last dose + 30-day safety follow-up period], OS date, DCO) – date of first dose + 1
- Time to the AE (days) calculated as date of first occurrence of the AE – date of first dose + 1 (in days), imputed AE start dates can be used in case of missing start dates.

The formula for calculating the event rate for a specific PT is as follows:

CCI

CCI

CCI

AEs will be assigned CTCAE grades (National Cancer Institute CTCAE version 4.0) and summaries of the number and percentage of patients will be provided by maximum reported CTCAE grade, SOC, PT and actual treatment group. Tabulation will be repeated to present AEs with a CTCAE grade 3 or higher and separately those AEs, causally related to study treatment by SOC and PT. Fluctuations observed in CTCAE grades within the same PTs during study will be listed.

Tabulation of AEs causally related to study treatment will be summarised by SOC and PT and presented by treatment group.

Summaries of the number and percentage of patients with AEs leading to dose modification of olaparib/placebo and also separately with AEs leading to dose reductions and drug interruptions of olaparib/placebo will be presented by PT and treatment group.

A summary table will be prepared presenting AEs which started prior to first dose or > 30 days following date of last dose by SOC and PT. Data will be presented by treatment group.

Death

A summary of all AEs resulting in deaths will be provided with number and percentage of patients by actual treatment group, categorised as:

- Related to disease under investigation
- AE outcome=death
- Both related to disease under investigation and with AE outcome=death
- AE with outcome=death ≥ 30 days after last treatment dose
- Deaths ≥ 30 days after last treatment dose, unrelated to AE or disease under investigation
- Patients with unknown reason for death

In addition, AEs with outcome of death will be summarised. The following summary tables will be prepared and presented by treatment group:

- By SOC and PT
- Causally related to study treatment by SOC and PT
- Death will be listed as part of TLFs for part 11 of the CSR

Serious AEs

The following SAE summaries and listings will be prepared. Summaries will be presented by treatment group:

- By SOC and PT
- Causally related to study treatment by SOC and PT
- Listing of key information

Discontinuation

AEs leading to discontinuation of study treatment will be summarised by SOC and PT. In addition, AEs leading to discontinuation of study treatment, causally related to study treatment will be summarised by SOC and PT. Details of AEs leading to discontinuation will be presented in a by-patient table.

Listings

By-patient listings will be produced as following:

- A by-patient listing of AEs, including flags for AESIs
- A by-patient listing of AEs causally related to olaparib
- A by-patient listing of SAEs
- A by-patient listing of AEs with CTCAE grade 3 or higher (separately for causally related to olaparib)
- A by-patient listing of AEs leading to dose reduction or dose interruption
- A by-patient listing of AEs presenting any events that occur prior to dosing or starting more than 30 days after discontinuing therapy

Laboratory assessments

Laboratory data is collected by local laboratories. Results will be converted to standard units for reporting purposes. Reference ranges from the local laboratories are collected in the CRF and will be used to determine reference range indicators (low, normal, high). If the same parameter is found as measured in serum and in plasma, then the summaries will not distinguish between them (e.g. values from plasma Albumin and serum Albumin will be summarised under Albumin). If the same parameter is found as measured in serum and in plasma within the same patient, which would be a rare case, then the change from baseline will only be calculated for those post-baseline values using the same source, i.e. only within plasma or serum. If one patient has multiple toxicity grades, because they are derived separately from serum and plasma, then the maximum value of the two will be considered.

For all continuous laboratory assessments, absolute value, change from baseline and percentage change from baseline will be summarised using descriptive statistics at each scheduled assessment time by actual treatment group.

Shift tables for laboratory values (excluding electrolytes) from baseline to worst value on-treatment categorized using the common toxicity criteria (CTC) grading based on local reference ranges will be produced. On-treatment is defined as data collected up until the last dose of olaparib/placebo. For parameters with no CTC grading, shift tables from baseline to worst value on-treatment will be provided using normal ranges for categorization. Shift tables for urinalysis values from baseline to worst grade on-treatment will also be provided.

Box-plots of absolute values for continuous laboratory assessments will be presented, with AZ project defined reference ranges indicated.

A scatter plot of alanine aminotransferase (ALT) versus total bilirubin, both expressed as multiples of the upper limit of normal (ULN), will be produced with reference lines at $3 \times \text{ULN}$

for ALT, and $2 \times \text{ULN}$ for total bilirubin. The scatter plot will be repeated for aspartate aminotransferase (AST) versus total bilirubin with reference lines at $3 \times \text{ULN}$ for AST, and $2 \times \text{ULN}$ for total bilirubin. In each plot, total bilirubin will be in the vertical axis.

Liver biochemistry test results over time for patients who show elevated ALT or aspartate aminotransferase (AST) ($\geq 3 \times \text{ULN}$) and elevated total bilirubin ($\geq 2 \times \text{ULN}$) (elevated results do not need to be present at the same visit), or a total bilirubin of $\geq 5 \times \text{ULN}$ will be tabulated and plotted.

All laboratory summaries and listings will be presented by actual treatment group.

By-patient listings of laboratory assessments will be provided showing at least: laboratory parameters, actual time point, measurements/results, CTC grade (if available), and the change from baseline value (for continuous data) (if appropriate). In addition, a flag will indicate if the value was out of normal range, if appropriate:

- Laboratory reference ranges
- Haematology
- Serum chemistry
- Urinalysis
- Individual patient data with elevated ALT or AST plus total bilirubin
- Pregnancy report data

Electrocardiograms

If available, overall evaluation of ECG will be summarised by visit as normal, abnormal or borderline.

All ECG data will be listed by actual treatment group.

Vital signs

Vital signs (systolic blood pressure [SBP], diastolic blood pressure [DBP], pulse rate, body temperature and weight) will be summarised by time point in terms of absolute values, changes from baseline and percentage changes from baseline at each scheduled measurement by actual treatment group. A shift table comparing baseline to maximum value on treatment will be summarised for SBP, DBP and pulse rate by actual treatment group, using the following normal ranges: SBP = 100 - 160 mmHg; DBP = 60 - 95 mmHg; pulse rate = 55 - 95 bpm.

Box plots for absolute values in SBP, DBP, pulse rate, body temperature, and weight will be presented.

Vital signs data will be listed.

Other

- Any concomitant procedures patients experiencing during the study will be listed in a by-patient listing
- Patients experiencing a Hy's Law incident will be tabulated and details will be included in by-patient listings. Hy's Law incidents are those cases where a patient shows an AST or ALT $\geq 3 \times \text{ULN}$ or total bilirubin $\geq 2 \times \text{ULN}$. Please refer to Appendix D of the CSP for further instructions.

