3.4.1 Adverse events

Adverse events and SAEs will be collected throughout the study, from informed consent until 30 days after the last dose of olaparib/placebo. Any untoward event occurring subsequent to the 30-day follow-up AE reporting period that the investigator assesses as possibly related to the study treatment should also be reported as an AE.

Adverse Event of special interest

Some AEs that follow clinical concepts are considered as adverse events of special interest (AESIs). They are grouped into the following three categories: Myelodysplastic syndrome / acute myeloid leukemia (MDS/AML), new primary malignancies and pneumonitis. An AstraZeneca medically qualified expert after consultation with the Global Patient Safety Physician will confirm the list of AEs of special interest (group terms and the specific preferred terms) and provide them for analysis. They will be confirmed at the BDRM prior to the final analysis for PFS and at the DRM prior to the final analysis of OS and PFS2.

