- Age calculation after randomisation: In order to identify reference ranges for laboratory parameters during the study, the age of a patient needs to be calculated at the timepoint of the collection of the sample. If the date of birth of a patient is only partially collected, then the following rule will be applied: (a) if only day is missing, then calculate age using the first day of the month; (b) if day and month are missing, then calculate age using the first of July. Then use the maximum of this calculated age and of the age as collected at screening for identification of reference ranges. If the date of birth is completely missing, then age as collected will be used.

Imputation of missing dates

For **AEs**, imputation methods will be used on completely missing start dates. Missing AE stop dates are not imputed. Imputation for partial dates is not applicable because partial adverse event dates are not collected in this study. Imputed start dates are used to decide if an observation is treatment emergent and for calculation of the AE event rates. Data listings will show actual date values. Missing AE start dates will be imputed with the first dose date unless the end date indicates it started prior to first dose date, in which case impute the 1st January of the year where the AE stopped as the start date.

For **concomitant medications**, start and stop dates are captured on the CRF with no partial dates being entered in the CRF. If the drug started prior to study start, then this is indicated by a flag “Yes” and the start date is missing. If the treatment with the medication continues, then this is indicated by a flag “Yes” and the stop date is missing. For the analysis of medications, it is required to decide if the medication was taken during the time of study treatment. Such a medication may have started before, on or after the first dose of study drug and was taken in the time frame up to and including 30 days following the last dose of study drug. For patients on study treatment at the time of the PFS analysis, the DCO date will be used as the last dose of study drug.

Therefore, medications are considered as treatment emergent (taken during study treatment) if they:

- started on or before first dose and (stopped on or after first dose or are ongoing) OR
- started after first dose but prior to or on date of last dose plus 30 days.

The following conservative imputation rules will be applied:

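### Treatment emergence is decided by AE start date alone, so an AE that begins in screening and worsens on study drug is left out of the standard on-treatment AE tables

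*SAP*

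**What the plan says.** **Collection.** SAP section 3.4.1: "Adverse events and SAEs will be collected throughout the study, from informed consent until 30 days after the last dose of olaparib/placebo". Table 12 narrows this. Screening Part 1 takes only procedure-related SAEs, and general AE recording opens with Screening Part 2, which runs from Day -28.

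**Summary window.** Section 4.2.13 labels AEs before Study Day 1 as pre-treatment. They "will be included in the AE listings, but will not be included in the summary tables", with a bracketed proviso that allows exceptions where stated. It adds: "The summary tables will include all AEs that occurred after the start of treatment up until the end of the 30 day follow-up period".

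**Deciding variable.** Section 3.4.9, on missing dates: "Imputed start dates are used to decide if an observation is treatment emergent and for calculation of the AE event rates".

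**Events outside the window.** Section 4.2.13 plans one further table, by SOC and PT, for AEs with onset before first dose or more than 30 days after last dose. On changes in grade it says only: "Fluctuations observed in CTCAE grades within the same PTs during study will be listed".

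**Outputs with no start-date limit.** Section 4.2.13 also plans a categorised summary of AEs resulting in death, with categories reaching beyond 30 days after last dose, and a by-patient table of AEs leading to discontinuation. Neither is restricted by onset date.

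**The concern.** Section 1.2 has patients start study treatment 4 to 8 weeks after their last dose of platinum-based chemotherapy, and AE recording is open during the weeks before first dose. An AE recorded in that interval can still be present on Day 1 and get worse on study drug. A rule based on start date treats that worsening as if it belonged to the period before treatment.

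Safety is summarised descriptively, without formal analysis, so the AE tables are the safety result. If an AE that reached grade 3 or ended treatment on study drug is missing from the tables where a reader looks for it, tolerability is overstated. If one arm has more such worsening than the other, the comparison between arms is distorted as well.

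**Working it through.** The SAP gives no figure for this point, so the check is mainly a reading of the rules.

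**1. Which events are exposed.** Onset lies between the opening of Screening Part 2 (Day -28) and first dose, the AE is still present at first dose, and the later worsening is kept on the same record.

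**2. Where such an event goes.** Take a non-laboratory AE that is grade 1 at first dose, reaches grade 3 on study drug and leads to discontinuation.

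| Output in section 4.2.13 | Included as written? |
|---|---|
| All AEs; maximum CTCAE grade; grade 3 or higher | No: onset precedes Day 1 and no exception is stated |
| SAEs; dose modification, reduction or interruption | No: same reason |
| AEs leading to discontinuation, by SOC and PT | No: same reason |
| Fatal AEs, by SOC and PT | No exception stated; scope unclear beside the death summary |
| Out-of-window table, by SOC and PT | Yes, but the plan specifies no grade, action taken or outcome |
| Listings, including CTCAE fluctuations | Yes |
| Categorised death summary; by-patient discontinuation table | Yes where relevant: no start-date limit stated |

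The proviso in 4.2.13 does not rescue the tables marked No, because none of them is named as an exception.

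**3. Event rate.** Section 4.2.13 sets time to AE = date of first occurrence - date of first dose + 1.
- Onset 28 days before first dose: -28 + 1 = -27 days.
- Onset the day before first dose: -1 + 1 = 0 days.

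Every pre-dose onset gives zero or a negative time. If the patient is instead handled as having no such event, the numerator loses one patient and the denominator gains that patient's full duration of therapy. Both changes lower the rate.

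**4. How the SAP treats other data that straddle first dose.**
- Concomitant medications (3.4.9): a medication begun on or before first dose and continuing past it counts as taken during treatment.
- Laboratory data (4.2.13): shift tables compare baseline with the worst on-treatment value.
- AEs: no equivalent rule, although the plan expects grades to fluctuate within a PT and arranges to list this.

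**5. Scale.** Section 1.3 gives about 145 patients randomised 3:2.
- Olaparib: 145 × 3/5 = 87. Placebo: 145 × 2/5 = 58.
- One omitted patient on olaparib: 1/87 = 1.1 percentage points.
- One omitted patient on placebo: 1/58 = 1.7 percentage points.

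This assumes that all randomised patients are dosed. The SAP gives neither the frequency of pre-dose AEs nor the proportion that worsen, so the total cannot be derived.

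**The case against.** **The effect may be nil.** If sites open a new AE record whenever an AE worsens, the new record has an on-treatment start date and is counted. The SAP does not say whether they do. The protocol, which is not at hand, may. This stands as a limit on size, but it does not supply an analysis rule: the SAP itself expects grades to change within a PT and plans only to list the changes.

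**The start-date reading rests partly on a missing-data rule.** The wording in 4.2.13 speaks of when an AE occurs, and the explicit link between start date and emergence is in the imputation text of 3.4.9. That is fair, but the out-of-window table in 4.2.13 is also defined by start date, and no other criterion is given.

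**Residual chemotherapy toxicity may rarely be captured this way.** General AE recording opens only at Day -28, and treatment starts at least 4 weeks after the last chemotherapy dose. Toxicity that began during chemotherapy will therefore generally predate AE recording, and may never become a pre-dose AE record. This stands: a reader might infer that pre-dose AE records will be common, and the SAP does not show it.

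**Blood counts are already covered.** The laboratory shift tables show worsening from baseline to worst on-treatment CTC grade whatever the AE onset. This stands too, and leaves non-laboratory AEs and the action-based tables as the main gap.

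**Changing the definition now has a price.** DCO1 has been analysed and the study unblinded, so a new definition at DCO2 would break comparability unless both are shown.

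**Conclusion.** The point holds for the standard on-treatment tables and the event rate. Followed as written, the SAP leaves out an AE that starts before first dose and then increases in grade, becomes serious, or leads to dose modification or discontinuation on study drug.

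Three stronger readings are tempting and are not supported:
- That such an event vanishes from every AE output, including when it is fatal. The categorised death summary and the by-patient discontinuation table carry no start-date limit, and the listings and out-of-window table retain the event.
- That a percentage under-count can be stated. Any such figure would rest on assumed rates that the SAP does not give.
- That the loss is larger on olaparib. That would follow only if olaparib worsens existing AEs more than placebo, which the document does not show.

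The conclusion rests on two assumptions: that a worsening stays on its original AE record, and that no unseen document defines emergence differently. The matter affects the completeness of the safety tables, not the efficacy analyses, and it is cheap enough to settle that the SAP should do so.

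**What to change.** In section 4.2.13:

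1. Define a treatment-emergent AE as one that starts, or whose CTCAE grade or seriousness increases over its pre-dose level, between first dose and the end of the 30-day follow-up.
2. Use the maximum on-treatment grade in the grade tables.
3. State that the SOC/PT tables of SAEs, dose modifications, discontinuations and fatal AEs include any AE with that consequence on or after first dose, whatever its start date. This also aligns the fatal-AE tables with the categorised death summary.
4. In the event rate, use the date of first worsening for such AEs where that date is collected. The SAP plans a listing of grade fluctuations but does not show that their dates are recorded, so this needs checking before the rule is written.

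The cost is a short text change and modest programming at DCO2. Counts would differ slightly from the DCO1 tables. Because the change comes after unblinding, it should be recorded as such, with a footnote explaining the difference or with both definitions shown.
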